ClinicalTrials.gov Cover Page

Title: Impact of Evolocumab (Repatha) in Cardiac Transplant Patients with Coronary Allograft Vasculopathy (CAV)

ID: NCT03944577

Document date: 01.01.2022

Document: Study Protocol and Statistical Analysis Plan

Eligibility Criteria

Inclusion criteria

- Heart transplant patients 19-80 years of age
- Coronary allograft vasculopathy documented by left heart cardiac catheterization
- Able to provide signed informed consent

Note: Evolocumab will be given as add-on therapy to heart transplant patients with CAV. Patients already on statin or other lipid lowering therapy are eligible for enrollment.

Exclusion criteria

- Rejection requiring IV therapy in the prior 3 months
- Infection requiring IV therapy in the prior 3 months
- Active liver disease or hepatic dysfunction, defined as aspartate aminotransferase (AST) or alanine aminotransferase (ALT) > 3 times the upper limit of normal
- Current or recent use of a PCSK9 inhibitor within the past 12 weeks
- Dual organ transplant recipient other than heart/kidney
- Renal dysfunction defined as GFR < 20 ml/min
- Known allergy to evolocumab or its components

Randomization/Registration Procedure

Heart transplant patients will be recruited for participation solely from the University of Nebraska Heart Transplant clinic. Our program provides care for approximately 330 heart transplant patients in total, and currently performs 40-50 heart transplants per year. Of these, over 40 patients already have a known diagnosis of CAV with more expected to be diagnosed in the coming year.

Heart transplant patients with CAV will be identified by the primary investigator and the transplant cardiology team. Eligible individuals will then be invited to participate (by phone call or during a clinical appointment) by the transplant cardiology research team. Interested patients will then be referred to trained personnel for informed consent, screening and study enrollment. Coordination is expected between study enrollment and a standard post-transplant clinic appointment to facilitate participation.

This study will be an open label, single cohort study. No randomization of patients or treatment blinding will occur. Enrollment is expected to take one year, with an additional one year of follow-up resulting in a total study duration of two years.

Research Study Design

Standard post-transplant care

Heart transplant patients with CAV who primary transplant followup care at the University of Nebraska will serve as the study cohort. Given the complexity of heart transplant patients, care is highly-protocolized and organized according to graft age. Care is most intensive in the first year following transplant wherein patients are initially evaluated on a weekly basis for the first month with reduced frequency (biweekly \rightarrow monthly \rightarrow quarterly) based on clinical progress over the first year. During year 2 post transplant, stable post-transplant patients are typically seen quarterly and this extends to biannual evaluations during year 3. After 3 years, stable post-transplant patients can often be seen on an annual basis. Thorough evaluations are completed annually including comprehensive labwork (complete blood count, complete metabolic panel, fasting lipid panel, thyroid function tests, hemoglobin A1c, creatinine kinase, urine protein analysis), assessment for donor specific antibodies, and imaging/testing. Imaging/testing includes an annual echocardiogram and chest x-ray as well as other imaging (DEXA scan, carotid and abdominal ultrasounds) at frequencies determined by comorbidities. Immunosuppression is maintained with calcineurin inhibitors (primarily tacrolimus) and DNA synthesis inhibitors (mycophenolate mofetil, mycophenolic acid or azathioprine). Patients are switched to mTOR inhibitors (primarily sirolimus) if significant renal dysfunction develops or CAV is diagnosed. High dose steroids are started at the time of transplant and typically weaned off during the first year. Calcineurin inhibitors and mTOR inhibitors are dosed according to trough serum levels, and thus monitored at least every three months indefinitely.

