Assess the effect of evolocumab on CAV progression. All patients enrolled will have CAV documented by cardiac angiography. Standard post-transplant care includes annual angiograms in patients diagnosed with CAV to monitor for disease progression. CAV progression will be defined as an increase of one CAV grade (CAV-1 \rightarrow CAV-2 or CAV-2 \rightarrow CAV-3). The number of patients with CAV progression of at least one grade while on evolocumab will be compared to historical controls for our transplant program. Percentage diameter stenosis for each vessel with visible CAV also will be determined by quantitative coronary angiography (QCA) using Philips Xcelera software package in a blinded fashion by an experience interventional cardiologist for patients angiograms completed one year prior to study entry, at study entry, and study conclusion. Angiographic change while on evolocumab therapy will be compared to the preceding year.

Assess the effect of evolocumab on immunosuppression regimens and graft rejection. Transplant patient are maintained on lifelong immunosuppression. These agents are prone to significant drug-drug interactions which can limit therapies. Serum levels of immunosuppression are monitored every three months per standard protocol. Measured serum levels at 3, 6, 9, and 12 months, as well as the number of dose adjustments while on evolocumab therapy while on evolocumab therapy will be compared to the preceding year. Statistical adjustment for confounding factors such as changes in renal function or other drugs known to alter immunosuppression levels (i.e. diltiazem, certain antimicrobial drugs) will be completed. In addition, the incidence of transplant rejection will be documented while on evolocumab therapy and compared to the prior year. Transplant rejection will be defined as symptoms requiring therapeutic intervention or endomyocardial biopsy findings of ≥grade 2 or positive C4d staining or new donor specific antibodies.

Measure the effect of evolocumab on serum lipids including HDL and triglycerides after 1 year of therapy. Fasting lipid profiles (total cholesterol, LDL, HDL and triglycerides) after 52 weeks of evolocumab therapy will be compared to baseline levels. Fasting lipid profiles are assessed annually as part of routine post-transplant care. The percentage change of LDL, HDL and triglyceride from baseline will be calculated after 1 year of evolocumab therapy.

Statistical analysis is detailed in Section 8 below.

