All suspected unexpected serious adverse reactions (SUSARs) related or possibly related to evolocumab and their follow-up reports will be reported to Amgen within 24 hours of submission to the regulatory agency or IRB. Amgen will be informed of any pregnancy occurring and/or existing during exposure to the investigational medicinal

product and pregnancies occurring in the partner of a patient participating in the study and potential infant exposure within ten (10) calendar days of sponsor awareness.

Section 8. Statistical Analysis Plan

Statistical analysis will be completed with the direct assistance of faculty from the University of Nebraska biostatistics department. Sample size (n=40) is chosen based on the size of the heart transplant clinic (the number of heart transplant patients with CAV expected to be eligible for study participation).

The primary outcome is percentage change from the baseline in LDL levels after 12 weeks of evolocumab therapy. Prior trials have demonstrated that evolocumab lowers LDL cholesterol at week 12 by greater than 50% from baseline[2, 3]. The sample size of n=40 is expected to yield greater than 99% power to detect 50% reduction of LDL cholesterol from baseline after 12 weeks of evolocumab therapy at a significance level of 0.05 using a two-sided Wilcoxon signed-rank test, assuming the estimated standard deviation of reduction of 0.17.

Descriptive statistics will be presented as frequencies and percentages for categorical variables, and mean ± standard deviation, or median with range for continuous variables, unless otherwise indicated. Paired t-tests or Nonparametric Wilcoxon signed-rank tests will be completed where appropriate to compare the primary endpoint before and after 12 weeks of evolocumab therapy, and compare continuous secondary endpoints after 1 year of evolocumab therapy to baseline. A linear mixed model analysis will be conducted to analyze immunosuppression serum levels measured at baseline, 3 months, 6 months, 9 months, and 1 year of evolocumab therapy. The binary secondary endpoint of CAV progression will be assessed after 1 year of evolocumab therapy using McNemar tests. Safety data will be reported with frequencies and percentages. All tests will be two-tailed. A p-value <0.05 will be considered significant. Analysis will be performed using SAS version 9.4 (SAS Institute, Cary, NC).

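### An immunosuppressant switch triggered by CAV diagnosis can fall in either year of the preceding-year comparison, and the planned analyses have no term to separate it from evolocumab

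*Combined protocol and SAP*

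**What the plan says.** - **Switch rule** (Research Study Design, standard post-transplant care): "Patients are switched to mTOR inhibitors (primarily sirolimus) if significant renal dysfunction develops or CAV is diagnosed". The same paragraph says that calcineurin inhibitors and mTOR inhibitors are both dosed to trough level and monitored at least every three months.
- **Recruitment pool** (Randomization/Registration Procedure): "over 40 patients already have a known diagnosis of CAV with more expected to be diagnosed in the coming year". Enrolment is expected to last one year, in a single open-label cohort without a concurrent control.
- **Eligibility**: CAV must be documented by catheterization. The three-month look-backs concern rejection and infection needing IV therapy. None concerns time since CAV diagnosis or a change of immunosuppressant.
- **Timing**: catheterization is annual for the first five years, and enrolment is expected around the annual evaluation.
- **Comparison** (Secondary endpoints): serum levels at 3, 6, 9 and 12 months and "the number of dose adjustments while on evolocumab therapy while on evolocumab therapy will be compared to the preceding year". Adjustment is promised for confounders, with renal function and interacting drugs given as examples. Angiographic change by QCA is also set against the preceding year.
- **Analysis** (Section 8): "A linear mixed model analysis will be conducted to analyze immunosuppression serum levels measured at baseline, 3 months, 6 months, 9 months, and 1 year". No covariates and no term for agent are listed, and the model contains no preceding-year data. No test is named for dose-adjustment counts.

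**The concern.** The immunosuppression objective asks whether evolocumab disturbs drug levels or dosing. Each patient is his or her own control, so the answer depends on nothing else changing systematically between the two periods. Under the programme's own rule, the diagnosis that makes a patient eligible also changes the immunosuppressant.

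Suppose a patient is diagnosed at the annual catheterization and enrolled soon after. The titration of the new agent is then counted in the evolocumab year. For a patient diagnosed and switched some months before enrolment, the same titration is counted in the comparator year. Either way, a patient newly given an mTOR inhibitor may have no comparator level of that drug, and covariate adjustment cannot supply one.

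The QCA comparison is exposed in the same way, because a treatment change made in response to CAV can fall in one interval and not the other. At stake is whether a difference between years, or its absence, can be attributed to evolocumab.

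**Working it through.** **The plan's own figure.** Section 8 states: "The sample size of n=40 is expected to yield greater than 99% power to detect 50% reduction of LDL cholesterol from baseline", "at a significance level of 0.05 using a two-sided Wilcoxon signed-rank test", "assuming the estimated standard deviation of reduction of 0.17". The standardized effect is 0.50/0.17 = 2.94 and the noncentrality is 2.94 × √40 = 18.6, so power is essentially 100%. The claim reproduces. It concerns LDL only and has no bearing on this point.

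**Inputs for the illustration.**
- From the documents: n = 40, a paired before/after comparison, two-sided 0.05.
- Assumed, because the documents give no figures: routine adjustments are Poisson with mean 2 in each year; a share f of patients switches; each switch adds k = 2 or 4 adjustments; evolocumab has no effect; the test is a paired t-test.

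**Formula, all switches on one side of enrolment.** Mean shift = f × k. Variance of the paired difference is about 2 + 2 + k²f(1 − f), and the standard error is the square root of that variance divided by √40.
- f = 0.10, k = 2: shift 0.20; variance 4 + 4 × 0.09 = 4.36; SE = 2.088/6.325 = 0.330; ratio 0.61. With critical value 2.02, the rejection probability is about Φ(0.61 − 2.02) + Φ(−0.61 − 2.02) = 0.08.
- f = 0.25, k = 4: shift 1.00; variance 4 + 16 × 0.1875 = 7.0; SE = 2.646/6.325 = 0.418; ratio 2.39; rejection probability about Φ(0.37) = 0.64.

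Simulation gives 8% and about 68% for these two cases. The second formula value is a little low because the number of switched patients is fixed in the simulation.

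**Simulated false-positive rates (nominal 5%).**

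| Share switched | Patients of 40 | Mean shift, all on one side | Rate, all on one side | Rate, evenly split |
|---|---|---|---|---|
| 5% | 2 | 0.1 to 0.2 | 5-7% | 3-4% |
| 10% | 4 | 0.2 to 0.4 | 8-15% | 2-4% |
| 25% | 10 | 0.5 to 1.0 | 28-68% | 1-3% |

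The shift is positive if all switches follow enrolment and negative, with the same rates, if all precede it.

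**Even split.** The mean shift is zero, but the spread grows. At f = 0.25 and k = 4 the variance is 4 + 16 × 0.25 = 8, so the estimated SE is 2.828/6.325 = 0.447, against 2/6.325 = 0.316 without switches. The test becomes conservative, and a real evolocumab effect would be harder to see.

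**Choice of test.** At a 25% share with 4 extra adjustments, the signed-rank test gives about 61% where the paired t-test gives 68%.

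**Levels.** If the switch shifts a continuous level by 1 to 3 SD of the paired difference, the paired t-test rejects in 9-23% of runs at a 10% share.

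**Excluding switched patients** returns the rate to about 5% in every dose-adjustment scenario in the table.

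**The case against.** - **Few patients may be affected.** More than 40 patients already had known CAV, and "Sample size (n=40) is chosen based on the size of the heart transplant clinic", so the known pool could in principle fill the study. Some patients will have switched earlier because of renal dysfunction or an intravascular ultrasound finding. This stands: the share is unknown, and at 5% the distortion is negligible. It does not remove the point, because refusals and exclusions leave places for new diagnoses, and a recent switch within the known pool also counts.
- **The direction is not fixed.** A reader might infer that the bias always makes evolocumab look disruptive. The documents do not support that: they set no interval between diagnosis and enrolment, so a switch can load either year.
- **The objective may still be answerable in switched patients.** A reader might infer that it is not. The protocol lists calcineurin inhibitors and DNA synthesis inhibitors as maintenance and does not say which class the mTOR inhibitor replaces. If the calcineurin inhibitor continues, its troughs remain comparable across both periods. Section 8 also does not say that levels of different agents will be pooled; it is silent.
- **Adjustment is promised.** The listed confounders are examples, so adjusting for a switch is not ruled out. The fair criticism is that neither the Secondary endpoints text nor Section 8 specifies it.
- **The stakes are limited.** The plan calls secondary conclusions primarily hypothesis-generating. That restrains the severity but does not make the comparison interpretable.

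**Conclusion.** The point holds as a gap in the secondary analyses. The eligibility event triggers an immunosuppressant switch, nothing separates that switch from enrolment, and the planned comparisons do not distinguish agents. A switch can therefore be credited to evolocumab, or can mask an effect, depending on when it falls.

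The size cannot be fixed from the documents. Under the stated assumptions it runs from negligible (5% of patients switched, or switches evenly split) to serious (a quarter switched, all on one side). The 25% share is an illustrative upper case that no passage supports.

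The point does not reach the primary endpoint, which is a 12-week LDL change from baseline. It should be corrected, but it does not threaten the trial's main result.

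**What to change.** In the Secondary endpoints text and Section 8:

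1. Analyse trough levels separately by agent, using only patient-agent pairs in which that agent was taken in both the comparator and the evolocumab period.
2. Record the date of CAV diagnosis and of any agent switch. Report dose adjustments with switch-related changes shown separately. Do not drop them from the main count, since removing every titration step could hide a real effect on dosing.
3. Prespecify a sensitivity analysis of dose adjustments, and of the QCA preceding-year comparison, that excludes patients switched between the start of the comparator year and study end.

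The cost is SAP wording and use of drug, dose and trough records from routine monitoring. The downside is fewer patients in the by-agent and sensitivity analyses of an already small cohort. Eligibility, patient care and the primary LDL analysis do not change.

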Study participation is expected to coordinate with the standard care of heart transplant patients. As most patients with CAV are more than 2 years post-transplant, enrollment will likely occur around the patient's annual clinical evaluation. Female patients of childbearing potential will undergo pregnancy testing prior to or during the screening/enrollment visit before study drug administration. Informed consent and baseline documentation will be completed by research personnel at the patient's annual evaluation when feasible.

Enrolled study participants will be treated with evolocumab (Repatha) 140 mg injected subcutaneously every 2 weeks for 52 weeks. All study participants will receive instruction on correct self-administration by research pharmacists. Study drug will be distributed to patients via courier or Fed Ex temperature-controlled coolers by the research pharmacy. The evolocumab dose (140 mg every 2 weeks) will remain constant for the duration of the study. Side effects will be assessed on a quarterly basis. Serious adverse events considered related to treatment, death, and pregnancy will all result in immediate discontinuation of the study drug.

Primary endpoint – LDL percentage change after 12 weeks of evolocumab therapy.

The primary objective of this study is to measure the impact of PCSK9 inhibition via evolocumab on serum LDL in heart transplant patients with CAV after 12 weeks. Similar to prior phase 2 trials investigating evolocumab, LDL change will serve as the primary endpoint providing a direct benchmark for comparison of heart transplant

patients. Baseline LDL will be obtained at study enrollment, likely with the patient's annual clinical evaluation. After 12 weeks of therapy, a fasting serum lipid profile will be obtained for measurement of LDL and assessment of the primary endpoint. Statistical analysis is detailed in Section 8 below.

Secondary endpoints

Assess the effect of evolocumab on CAV progression. All patients enrolled will have CAV documented by cardiac angiography. Standard post-transplant care includes annual angiograms in patients diagnosed with CAV to monitor for disease progression. CAV progression will be defined as an increase of one CAV grade (CAV-1 \rightarrow CAV-2 or CAV-2 \rightarrow CAV-3). The number of patients with CAV progression of at least one grade while on evolocumab will be compared to historical controls for our transplant program. Percentage diameter stenosis for each vessel with visible CAV also will be determined by quantitative coronary angiography (QCA) using Philips Xcelera software package in a blinded fashion by an experience interventional cardiologist for patients angiograms completed one year prior to study entry, at study entry, and study conclusion. Angiographic change while on evolocumab therapy will be compared to the preceding year.

Assess the effect of evolocumab on immunosuppression regimens and graft rejection. Transplant patient are maintained on lifelong immunosuppression. These agents are prone to significant drug-drug interactions which can limit therapies. Serum levels of immunosuppression are monitored every three months per standard protocol. Measured serum levels at 3, 6, 9, and 12 months, as well as the number of dose adjustments while on evolocumab therapy while on evolocumab therapy will be compared to the preceding year. Statistical adjustment for confounding factors such as changes in renal function or other drugs known to alter immunosuppression levels (i.e. diltiazem, certain antimicrobial drugs) will be completed. In addition, the incidence of transplant rejection will be documented while on evolocumab therapy and compared to the prior year. Transplant rejection will be defined as symptoms requiring therapeutic intervention or endomyocardial biopsy findings of ≥grade 2 or positive C4d staining or new donor specific antibodies.

Measure the effect of evolocumab on serum lipids including HDL and triglycerides after 1 year of therapy. Fasting lipid profiles (total cholesterol, LDL, HDL and triglycerides) after 52 weeks of evolocumab therapy will be compared to baseline levels. Fasting lipid profiles are assessed annually as part of routine post-transplant care. The percentage change of LDL, HDL and triglyceride from baseline will be calculated after 1 year of evolocumab therapy.

Statistical analysis is detailed in Section 8 below.

Regulatory oversight

The study will be conducted under the oversight of the University of Nebraska IRB. An independent University of Nebraska Medical Center Data Safety and Monitoring Board (DSMB) will be established to monitor participant safety, data quality and evaluate the progress of the study.

Drug Formulation and Procurement

Study drug (evolocumab) will be provided by Amgen Inc. While evolocumab is commercially available and FDA approved for patient use, storage and distribution in this study will be managed by research pharmacy staff at the University of Nebraska. Study drug will be stored by research pharmacy staff who will distribute it to patients. Study participants receive study drug quarterly directly from research pharmacy staff or via courier in temperature-controlled KoolTempGTS coolers (Cold Chain Technologies, Franklin, Massachusetts). Drug accountability will be managed by research pharmacists as well.

Toxicity and Adverse Event Reporting Guidelines

Evolocumab is currently FDA-approved and commercially available for patient use in the United States. Currently used in patients for the secondary prevention of cardiovascular disease and treatment of primary hyperlipidemias, adverse event data is available from greater than 27,000 patients enrolled in clinical trials. Clinical experience has shown evolocumab to be well-tolerated with minimal adverse events (see Tables 4 and 5 below).

Adverse events will be assessed by research personnel at week 2, 4, 12, 26, 38 and study conclusion (52). Events will be obtained either by phone survey or during a standard-of-care clinic visit. Data will be stored and managed using the Forte Electronic Data Capture (EDC) software system. Adverse events will be collected using the Common Terminology Criteria for Adverse Event (CTCAE) version 5.0 forms. Adverse events will be quantified and presented by organ system. Reported events will be cataloged and reported to the University of Nebraska IRB and Amgen annually and at the conclusion of the study by research personnel. Reported events will be independently reviewed by a cardiology faculty member with significant experience prescribing PCSK9 inhibitors.

All suspected unexpected serious adverse reactions (SUSARs) related or possibly related to evolocumab and their follow-up reports will be reported to Amgen within 24 hours of submission to the regulatory agency or IRB. Amgen will be informed of any pregnancy occurring and/or existing during exposure to the investigational medicinal

product and pregnancies occurring in the partner of a patient participating in the study and potential infant exposure within ten (10) calendar days of sponsor awareness.

Section 8. Statistical Analysis Plan

Statistical analysis will be completed with the direct assistance of faculty from the University of Nebraska biostatistics department. Sample size (n=40) is chosen based on the size of the heart transplant clinic (the number of heart transplant patients with CAV expected to be eligible for study participation).

The primary outcome is percentage change from the baseline in LDL levels after 12 weeks of evolocumab therapy. Prior trials have demonstrated that evolocumab lowers LDL cholesterol at week 12 by greater than 50% from baseline[2, 3]. The sample size of n=40 is expected to yield greater than 99% power to detect 50% reduction of LDL cholesterol from baseline after 12 weeks of evolocumab therapy at a significance level of 0.05 using a two-sided Wilcoxon signed-rank test, assuming the estimated standard deviation of reduction of 0.17.

Descriptive statistics will be presented as frequencies and percentages for categorical variables, and mean ± standard deviation, or median with range for continuous variables, unless otherwise indicated. Paired t-tests or Nonparametric Wilcoxon signed-rank tests will be completed where appropriate to compare the primary endpoint before and after 12 weeks of evolocumab therapy, and compare continuous secondary endpoints after 1 year of evolocumab therapy to baseline. A linear mixed model analysis will be conducted to analyze immunosuppression serum levels measured at baseline, 3 months, 6 months, 9 months, and 1 year of evolocumab therapy. The binary secondary endpoint of CAV progression will be assessed after 1 year of evolocumab therapy using McNemar tests. Safety data will be reported with frequencies and percentages. All tests will be two-tailed. A p-value <0.05 will be considered significant. Analysis will be performed using SAS version 9.4 (SAS Institute, Cary, NC).

Given the limited statistical power due to the small cohort, conclusions from secondary endpoints are expected to by primarily hypothesis-generating with data providing support for potential future studies.

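### Masked reading is stated for QCA stenosis but not for the CAV grade that defines progression, although a blinded cardiologist already reads the same patients' films

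*Combined protocol and SAP*

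**What the plan says.** Randomization/Registration Procedure sets the design: "This study will be an open label, single cohort study. No randomization of patients or treatment blinding will occur".

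Under Secondary endpoints, "CAV progression will be defined as an increase of one CAV grade", and the count of patients who progress "while on evolocumab will be compared to historical controls for our transplant program". No grader, masking or adjudication is given for this grade. A second measure follows: "Percentage diameter stenosis for each vessel with visible CAV also will be determined by quantitative coronary angiography (QCA" and so on. This measure is to be read "in a blinded fashion by an experience interventional cardiologist", "for patients angiograms completed one year prior to study entry, at study entry, and study conclusion". What the reader is blinded to is not stated.

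Table 3, under Standard post-transplant care, builds the grade mainly from stenosis cut-offs of 50% (left main) and 70% (primary vessels and branches). CAV-3 can also be reached through an ejection fraction of 45% or less, or restrictive physiology.

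Section 8 names McNemar tests for CAV progression and does not say who grades. It closes by describing conclusions from secondary endpoints as primarily hypothesis-generating, given the small cohort.

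**The concern.** Whether a patient counts as progressing can turn on one call: is a lesion just under or just over 50% or 70%? In an open-label single cohort every conclusion film comes from a treated patient. A grader who knows this may lean towards no progression on borderline films, and that error would favour evolocumab. With 40 patients the number of progressors is likely to be small, so a few such calls could move the result visibly.

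The plan protects the software-assisted measurement with a blinded reader and states no protection for the threshold call that defines the endpoint. At stake is how far the progression result can be believed, and whether it gives sound support to the later studies that Section 8 has in mind.

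**Working it through.** **1. The plan's own figure.** No rate, effect size or power is given for CAV progression. The only power statement concerns LDL: n = 40, reduction 0.50, SD 0.17, two-sided 0.05. By the normal approximation, 0.50 / (0.17/√40) = 18.6, and Φ(18.6 − 1.96) is about 1.000. This agrees with the stated figure of more than 99%. It has no bearing on CAV grading, and the fix leaves it unchanged.

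**2. What the blinding covers.** The blinding phrase sits in the sentence on percentage stenosis. That sentence presents QCA as an additional measure, after the grade endpoint and its comparator have been set out. Read in order, the blinding belongs to QCA. The grade is left with no statement either way.

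**3. What the blinded reader already handles.** Three films per enrolled patient: 40 × 3 = 120 at most. No blinded reading of historical-control films is described.

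**4. Size of the bias (illustration only).** Assume no drug effect, a true progression rate p0, and a share u of true progressions not called.

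Recorded progressors = 40 × p0 × (1 − u). At p0 = 20%:
- u = 0: 8 (20%)
- u = 25%: 8 × 0.75 = 6 (15%)
- u = 50%: 8 × 0.50 = 4 (10%)

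The apparent relative reduction equals u, so it is 25% or 50% here.

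**5. Effect on a comparison with a fixed historical rate.** Take an exact two-sided binomial test at 0.05 with n = 40. It rejects in favour of evolocumab at counts of 0 (p0 = 10%), 3 or fewer (20%) and 6 or fewer (30%). The chance of this is P(X ≤ c), where X is binomial with n = 40 and probability p0(1 − u). For p0 = 10% and u = 0 it is 0.90^40 = 1.5%.

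| p0 | u = 0 | u = 25% | u = 50% | calls lost at u = 25% |
|---|---|---|---|---|
| 10% | 1.5% | 4.4% | 12.9% | 1 |
| 20% | 2.9% | 13.0% | 42.3% | 2 |
| 30% | 2.4% | 17.3% | 60.7% | 3 |

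This is not the planned test. It shows only how few calls matter.

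**6. Effect on a paired comparison.** Suppose 8 patients progress in the preceding year and 4 are recorded in the study year. With k patients counted in both years, the discordant counts are 8 − k and 4 − k. Exact McNemar p runs from 2 × 794/4096 = 0.39 (8 against 4, k = 0) down to 2 × 0.5^4 = 0.125 (4 against 0, k = 4). The uncorrected chi-square version gives (4 − 0)²/4 = 4.0, p = 0.046, but only in that last case. At k = 3 it is (5 − 1)²/6 = 2.67, p = 0.10. In the paired analysis, then, bias of this size would mainly distort the estimate and would seldom produce significance.

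**The case against.** **The documents do not say that grading is unblinded.** A reader might infer that the grade comes from routine catheterization reports by staff who know the treatment and the timing of the film. That goes beyond the text. The protocol says that annual angiograms are standard care and that severity follows Table 3; it does not name the grader. What stands is that masking is unstated, so an aware grader is possible.

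**The fix does not repair the historical-control comparison.** This is correct. Masked cohort grades set against clinic-graded controls would create a new mismatch, and keeping the clinic grade leaves any reader-knowledge bias in place. Removing it would need control films read under the same masking, which the plan does not provide for. The cheap fix helps only the comparison with the preceding year.

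**A film-only grade would change the endpoint.** Also correct, if nothing else is done: progression to CAV-3 through ejection fraction or restrictive physiology would be lost. The fix has to carry that route separately.

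**The plan already has a safeguard.** Blinded QCA on the same films could reveal a divergence between grade and measured stenosis. This lessens the problem but does not mask the endpoint itself. The hypothesis-generating status and the laboratory primary endpoint also limit the consequences.

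**The size is assumed.** A reader might conclude that reader bias could account for a whole apparent benefit. The illustration yields that only because it assumes zero drug effect and one-directional under-calling.

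**Conclusion.** The point holds as a gap in the stated masking, with a cheap improvement available. Blinding is stated for QCA alone, the grade that defines progression has no stated grader or masking, and a blinded cardiologist already reads the enrolled patients' three films.

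The documents support no size for the bias. In the illustration, 8 true progressors in 40 become 6 or 4. This rests on an assumed 20% progression rate, an assumed 25% or 50% of calls withheld, all errors in one direction, and no drug effect.

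The point does not show that grading will be unblinded or that a favourable result would be an artefact. It concerns a secondary, hypothesis-generating endpoint, and the LDL primary endpoint is unaffected. The change is worth making because it is cheap.

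**What to change.** 1. State who assigns the CAV grade and what that person is masked to.
2. At the QCA sitting, have the blinded cardiologist also record the angiographic Table 3 grade for the prior-year, entry and conclusion films, with dates hidden and film order shuffled.
3. Apply the ejection-fraction and restrictive-physiology criterion for CAV-3 separately, from recorded data and by a rule fixed in advance, so that progression by that route still counts.
4. Use the resulting grade for a within-patient McNemar comparison of the evolocumab year with the preceding year, and say so explicitly. At present Section 8 names the paired test, while the endpoint text compares grade progression with historical controls.
5. Keep the clinic-assigned grade for the historical-control comparison, on the assumption that controls were graded clinically. State that this comparison remains open to reader-knowledge bias unless control films are read under the same masking.

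Cost: one extra field on at most about 120 films already being read, a short rule for the non-angiographic criterion, and two reported grades that may differ. No new reader, film or patient is needed, and sample size, significance level and power do not change. Reading control films under masking would be additional work and is optional.
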